Participants in Arm A (LBC cytology screening) will experience three screening rounds in the trial - Round 1 at baseline, Round 2 at 2.5 years, and Round 3 at 5 years. Participants in Arm B (HPV screening) will experience 2 screening rounds in the trial – Round 1 at baseline, and Round 2 at 5 years.

A 10% sample of HPV negative women in each strata of Arm B will be recalled at 2.5 years for cytology testing, for safety monitoring purposes (in order to allow safety monitoring data to be accrued earlier as the trial progresses, the initial randomization to safety monitoring will be increased to 20% of all women recruited from early-mid 2016 until sufficient women to result in an average 10% ratio randomised to safety monitoring have been recruited in each strata). The women recruited for safety monitoring are additional to the women recruited for the analysis of primary outcomes; i.e. this group will not be included in the analysis for the primary endpoint.

All women presenting for cervical screening or follow-up will be enrolled in the trial. All women will be randomized but if under current follow-up will be assigned to the appropriate management branch of the arm to which they are assigned. This approach is in line with Compass providing a sentinel experience for the National Cervical Screening Program transition in 2017, in which all women will need to transition to management under new pathways. A total of 36,300 women in the birth cohorts not offered vaccination and 84,700 women in the cohorts offered vaccination, who are presenting for routine screening, will be recruited, along with additional women to bring the total number recruited to 121,000 (with the additional women representing those presenting for routine follow-up (approximately 5%) and those recruited for a safety monitoring sample (10% of HPV screen negative participants presenting for routine screening)). The sample size requirements for the trial are based on assessment of the cumulative proportion of CIN3+ (including CIN3 and invasive cervical cancer) in women who were screen-negative at baseline.

Primary Outcome

Cumulative CIN3+ (Cervical Intraepithelial Neoplasia Grade 3 or invasive cervical cancer)

The primary outcome will be cumulative CIN3+ at 5 years following a 5-year HPV exit testing round in both arms, in women randomised to the HPV arm vs. women randomised to the LBC arm, adjusted for censoring after CIN2+ treatment.

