Upon receipt and logging of the sample at VCS Pathology, individual subject allocation to one of the study arms will be performed using a computer-generated randomisation sequence in a 1:2 ratio, stratified by age at recruitment (DOB <1st July 1980 and DOB ≥ 1st July 1980) (indicating whether or not offered HPV vaccination in the publicly-funded program). Secondary randomisation at a 1:1 ratio will be performed on samples which are allocated to study arm B (HPV DNA testing) and which are found to be other oncogenic HPV positive (not HPV 16/18) – this group will be randomised to receive either an LBC or dual-stained cytology triage test. A total of 10% of women in the HPV study arm will have early recall (at 2.5 years) for LBC testing for safety monitoring, should their primary HPV test result be negative.

Neither the participant nor the practitioner will be aware of subject allocation at the time of the recruitment visit and cervical sampling. Allocation will not be concealed in the laboratory (for reasons of practicality). The study allocation and test results will be communicated to the practitioner by means of a standard laboratory reporting form which will include the appropriate follow-up recommendation.

The randomisation schedule and process will be the responsibility of the NHMRC Clinical Trials Centre which has extensive experience in developing and managing the randomisation procedure for clinical trials.

Data Analysis Plan

Pre-specified analyses will be conducted at four time points. These will be done separately for each recruitment strata, as appropriate given the timing for when recruitment for each strata matures, and are as follows:

- 1. BASELINE and 12-month follow-up analysis**
Cross-sectional analysis of results from the baseline and 12-month follow-up screening rounds, including test positivity rates, colposcopy referral rates and CIN2+ and CIN3+ detection rates (*Secondary Objectives 4 and 5*).
- 2. 2.5 YEAR SCREENING ROUND ANALYSIS (Arm A)**
Cross-sectional analysis of CIN2+ and CIN3+ rates at the 2.5-year screening round (Arm A).
- 3. 2.5 Year SAFETY MONITORING ANALYSIS (Arm B)**
Cross-sectional analysis of CIN2+ and CIN3+ rates at the 2.5-year Safety Monitoring analysis (Arm B).
- 4. 5 YEAR FOLLOW-UP Following completion of trial follow-up at 5.5 years.**

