For women in whom the QC histopathology analysis indicates a previously undiagnosed CIN 2/3+ lesion, their primary practitioner will be made aware of the QC diagnosis. If the woman has not been referred for further evaluation or for treatment of high grade cervical precancerous disease since the biopsy in question was originally taken, the letter to the practitioner will recommend that further investigation is conducted and that treatment of a confirmed high grade lesion proceeds according to the new 2017 NCSP Guidelines [24]. In general terms, Compass participants who are treated for CIN 2+ disease will have post-treatment follow-up according to NCSP guidelines for HPV as “test of cure”, and at the point of treatment will be considered to have completed trial follow-up. Following completion of test of cure these women should return to the routine screening as recommended. Although this group of women will be censored from the main trial analysis from the time of treatment, routine follow-up through the VCCR and SACSR will continue, and the data will be collated as part of the trial, for safety monitoring purposes and supplementary analyses.

Procedure for managing off-protocol women

The lab will be guided by the following principles for managing women who are “off protocol”.

Both conventional cytology and LBC received: If both a conventional and LBC sample are received then the lab will process the LBC sample according the study protocol. The laboratory will then call the referring practitioner and seek their consent to not process the conventional smear. If the practitioner would like the conventional processed the lab will process conventional and LBC and report on both.

Conventional cytology received at 12-month, 24-month follow-up or at 2nd or 3rd round screening: In the event that a Compass participant has a conventional cytology smear collected, rather than the prescribed liquid based cytology (LBC), we will not request that practitioners recollect a LBC. Rather the sample will be read as a conventional smear and managed according to Study Arm A, regardless of what study arm the woman was originally assigned to. If the woman is in Study Arm A and screen negative she will be asked to return in 2.5 years for routine cytology screening using LBC. If the test is LSIL or HSIL, the woman is followed up according to the protocol schedule for Study Arm A.

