If a woman is in Study Arm B and negative, or LSIL she will be asked to return in 12 months for a HPV DNA test. If the result is HSIL, the woman is treated as higher risk and follows the protocol schedule (as per Study Arm A) for this result.

In the event that a Practitioner collects a conventional cytology they will be contacted by the Compass Register and reminded to collect LBC samples for all Compass women.

Conventional cytology received at colposcopy: If a conventional cytology sample is returned at colposcopy the sample will be read as a conventional smear and recommendations will be reported as usual.

Woman attends for screen early:

If a woman has been randomised to Study Arm A, the sample will be processed, and will be followed-up as per the protocol schedule for Study Arm A.

If a woman has been randomised to Study Arm B, and attends for an early re-screen, and the test result is negative (low-risk), follow-up will be according to the previous Compass test result.

If the cytology test is abnormal (LSIL or HSIL), the woman will be followed-up according to the protocol schedule for Study Arm A (intermediate and higher risk categories).

Opting-out of the trial

Participants will be informed at the time of consent that they will have the right to opt-out of the trial at any point. Participants will be able to opt-out of the trial by either calling VCS Pathology, the VCCR (Compass Hotline), the recruiting primary health care clinic or the relevant Human Research Ethics Committee (HREC). Instructions to the women on the participant information sheet will provide the study hotline as the primary suggested mechanism to opt out. Once a woman chooses to opt out of the trial, her details on VCS Pathology database (CIS) will be updated to reflect this and her Compass study flag will be changed to an opt-out flag. A similar opt-out of trial flag will be marked at the Compass Register. These women will subsequently be followed up by their local Pap test register consistent with National Cervical Screening Policy at the time.

Biobanking

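### The rule against recollecting after a conventional smear reaches the 5-year exit visit, so some women would have no HPV exit test before follow-up closes

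*Protocol*

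**What the plan says.** Under *Procedure for managing off-protocol women*, the protocol covers a participant whose practitioner sends a conventional smear in place of a liquid-based (LBC) sample. The rule is headed "Conventional cytology received at 12-month, 24-month follow-up or at 2nd or 3rd round screening" and states that "we will not request that practitioners recollect a LBC". The smear is read as conventional cytology and managed under Arm A rules whichever arm the woman is in. What follows depends on arm and result:

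- Arm A, negative: "she will be asked to return in 2.5 years for routine cytology screening using LBC".
- Arm B, negative or LSIL: "she will be asked to return in 12 months for a HPV DNA test".
- Arm A LSIL, and HSIL in either arm: the Arm A schedule for that result. These women are not part of this point.

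The section on the primary endpoint and sample size fixes the rounds. Arm A has "Round 1 at baseline, Round 2 at 2.5 years, and Round 3 at 5 years"; Arm B has "Round 1 at baseline, and Round 2 at 5 years". Under *Primary Outcome*: "The primary outcome will be cumulative CIN3+ at 5 years following a 5-year HPV exit testing round in both arms". The *Data Analysis Plan* times the final analysis as "Following completion of trial follow-up at 5.5 years", with the last six months allowed for histology results to arrive.

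**The concern.** Only Arm A has a third round, and it is the 5-year visit. Arm B's second round is also the 5-year visit. The heading therefore brings the exit visit under the no-recollection rule in both arms, and nothing in the section exempts it.

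Trial samples are collected in a liquid medium (*Screening and triage test technologies*). A visit that yields only a conventional smear leaves no trial sample for the HPV exit test. The primary outcome depends on that test being applied equally in both arms. For the women concerned, the rule puts a cytology reading in its place and then sets a different next test at a different time in each arm, after closure in both.

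The Arm A instruction also sits badly with *Recruitment post-Renewed National Cervical Screening Program*, where Arm A women have two cytology tests, then an HPV exit test, then 5-yearly HPV screening. The likely cause is drafting: the return intervals suit the earlier visits, and the exit round was not carved out.

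**Working it through.** **Timing.** Next test = visit time + return interval, compared with the 5.5-year close.

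| Visit with smear only | Next test due | Against 5.5 years |
|---|---|---|
| Arm B, 12 months, negative/LSIL | 1 + 1 = 2.0 y (HPV) | inside |
| Arm B, 24 months, negative/LSIL | 2 + 1 = 3.0 y (HPV) | inside |
| Arm A Round 2, negative | 2.5 + 2.5 = 5.0 y | inside |
| Arm A Round 3, negative | 5 + 2.5 = 7.5 y (LBC) | 2.0 y late |
| Arm B Round 2, negative/LSIL | 5 + 1 = 6.0 y (HPV) | 0.5 y late |

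The rule works at the earlier visits and fails only at exit.

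**The plan's own power figure.** Inputs from the primary endpoint section: control rate 0.6%, absolute margin 0.22 points, 97.5% confidence (one-sided 0.025), 10% non-compliance, 121,000 women. Allocation is 1:2 (*Randomisation*). Treating the 10% as loss leaves 121,000 × 0.9 = 108,900 women: 36,300 in Arm A and 72,600 in Arm B.

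- SE = √[0.006 × 0.994 × (1/36,300 + 1/72,600)] = 0.000496
- Power = Φ(0.0022/0.000496 − 1.960) = Φ(2.47) = 99.3%

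The stated power of more than 90% is reproduced. Removing a further 15% or so, for women in follow-up and in the safety sample, gives 98.3%.

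**Women affected.** The protocol gives no frequency of smear-only exit visits, so the share is an assumption. Taking 0.1% to 1%, with full return and nobody removed for the safety sample:

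- Arm A: 121,000/3 = 40,333 women, so 40 to 403 affected.
- Arm B: 80,667 women, so 81 to 807 affected.
- CIN3+ at 0.6%: 242 cases in Arm A and 484 in Arm B. Among affected women this is 0.2 to 2.4 and 0.5 to 4.8 cases.

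For a given share these are ceilings, because disease found earlier, or by the exit cytology itself, still counts.

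**Shift if one arm only is affected.** Ceiling = share × 0.6% = 0.0006 to 0.006 points. Divided by 0.22, this is 0.3% to 2.7% of the margin. Lost cases in Arm A make HPV screening look worse; lost cases in Arm B make it look better. With Arm A lowered by 0.006 points (the adverse case for non-inferiority), SE = 0.000495 and power = Φ((0.0022 − 0.00006)/0.000495 − 1.960) = Φ(2.37) = 99.1%.

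**A wider assumption.** Suppose 1% to 10% of exit visits are smear-only and 25% to 75% of CIN3+ is found only through the exit HPV test. The one-arm shift runs from 0.01 × 0.25 × 0.6 = 0.0015 points to 0.10 × 0.75 × 0.6 = 0.045 points, or 0.7% to 20% of the margin. At the upper end, with Arm A lowered to 0.555%, SE = 0.000484 and power = Φ((0.0022 − 0.00045)/0.000484 − 1.960) = Φ(1.66) = 95%.

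**The case against.** The strongest objection is that the situation will hardly arise. If an LBC sample arrives with the smear, it is processed, so only smear-only visits matter. The older cohort's recruitment target was met in early 2016, so its exits run to about early 2021. National recruitment begins in mid-2017, so those exits start around mid-2022. Both are more than three years after HPV testing replaces the Pap test in December 2017. Practitioners are also told with each result that an LBC sample is needed, and the Register contacts anyone who sends a conventional smear. This argument stands, and it is why the effect is taken to be small. It does not repair the text: the Register's contact is a reminder, while the rule expressly excludes asking for a new sample at the visit in question.

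Second, missed exit tests are foreseen: the analysis is by intention to treat, 10% non-compliance is allowed for, and the handling of missing exit tests may be left to the statistical analysis plan. That protects power. It does not make ascertainment equal between arms, and no analysis plan can supply an HPV result that was never obtained.

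Third, an off-protocol rule may properly differ from the planned pathway, so the mismatch with Arm A's move to 5-yearly HPV screening is secondary. That is fair. The main conflict is with the definition of the primary outcome.

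Fourth, 5.5 years might be read as a calendar point for the analysis. An early recruit's 6-year HPV test could then precede data lock, but it would still fall outside a 5-year endpoint.

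The fallback to national guidelines under *Other clinical circumstances* does not help, because it applies only to situations that the protocol does not address.

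**Conclusion.** The concern holds and is minor. Followed as written, a smear-only exit visit leaves Arm A women with a negative smear, and Arm B women with a negative or LSIL smear, without an HPV exit test inside follow-up. The next test is 2.0 years late in Arm A and 0.5 years late in Arm B.

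The timing follows directly from the text, reading the 5.5-year close per woman. The size does not: both ranges for the share of smear-only exits are assumptions, and the lower one (0.1% to 1%) fits better with exits that fall well after the programme change. On that range the comparison moves by no more than 2.7% of the margin. The direction depends on which arm the smears fall in and is unknown. The power claim is not in question. The case for acting is that the error lies at the visit that defines the endpoint and gives affected women the wrong next step, most plainly Arm A women sent back to cytology.

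**What to change.** - Limit the no-recollection rule to the 12-month and 24-month visits and Arm A Round 2.
- Add a sentence for a conventional smear at the 5-year visit (Arm A Round 3, Arm B Round 2): the Register, which already contacts the practitioner, requests an LBC sample for the HPV exit test, early enough for any histology to be reported by 5.5 years.
- After Arm A Round 3, replace the 2.5-year return for LBC with the HPV exit test, followed by 5-yearly HPV screening.
- Keep women with HSIL on the existing higher-risk pathway, with no wait for the HPV result.

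The cost is one heading phrase, one added sentence, the amended Arm A return instruction and revised wording in the Register's letter. The exit HPV test is already in the protocol. The downside is a second visit for the women affected: at the assumed 0.1% to 1%, at most 121 to 1,210 of 121,000.

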24. Cancer Council Australia Cervical Cancer Screening Guidelines Working Party. **National Cervical Screening Program: Guidelines for the management of screen-detected abnormalities, screening in specific populations and investigation of abnormal vaginal bleeding.** Sydney: *Cancer Council Australia*. [Version URL:

<http://wiki.cancer.org.au/australiawiki/index.php?oldid=167506>, cited 2017 Oct 24]. Available from: http://wiki.cancer.org.au/australia/Guidelines:Cervical_cancer/Screening.

Footnotes: Study arm A

- 1) Includes any glandular abnormality, possible HG endocervical glandular lesions and atypical glandular cells of uncertain significance.
- 2) If results at colposcopy are negative/CIN 1/HPV, women require one negative follow-up tests at 12 months, using index test, before returning to routine screening (return to original study arm). If CIN 2+/AIS: treatment and follow-up according to The NCSP guidelines. Colposcopy unsatisfactory: managed by the individual specialist, informed by The NCSP guidelines (see detailed management flow charts).
- 3) AIS will have Annual co-test (HPV and LBC) indefinitely. Refer to the National Pathology Accreditation Advisory Council (NPAAC) draft protocol, Chapter 11 Management of Glandular Abnormalities, Flowchart 11.4 follow up after excisional treatment for AIS.
- 4) LBC result to assist colposcopy reading they do not feed into the recommended follow-up for women
- 5) Concealed DS not for management of women

Footnotes: Study arm B

- 1) Includes any glandular abnormality, possible HG endocervical glandular lesions and atypical cells of uncertain significance.
- 2) If results at colposcopy are negative/CIN1/HPV, women require one negative follow-up tests at 12 months, using index test, before returning to routine screening (return to original study arm). If CIN 2+/AIS: treatment and follow-up according to The NCSP guidelines (see detailed management flow charts). Colposcopy unsatisfactory: managed by the individual specialist, informed by The NCSP guidelines (see detailed management flow charts).
- 3) AIS will have Annual co-test (HPV and LBC) indefinitely. Refer to the National Pathology Accreditation Advisory Council (NPAAC) draft protocol, Chapter 11 Management of Glandular Abnormalities, Flowchart 11.4 follow up after excisional treatment for AIS
- 4) LBC result to assist colposcopy reading they do not feed into the recommended follow-up for women
- 5) Concealed DS not for management of women
- 6) Configurable randomisation-may be adjusted during the trial

Version 1.3_10062016

¹ Structured reporting protocol for excisions and colposcopic biopsies performed for the diagnosis and treatment of pre-invasive cervical neoplasia, Royal Australasian College of Pathologists, 1st Edition, 2017.
